### 4.3. Protocol Deviations

Subjects who did not meet the eligibility criteria for study entry, but enrolled in the study will be summarized regardless of whether they were exempted by the sponsor or not. The summary will present the number and percentage of subjects who did not meet at least 1 eligibility (inclusion or exclusion) criterion and the number of subjects who did not meet specific criteria by treatment group based on All Randomized/Enrolled Analysis Set. A by-subject listing will be provided for those subjects who did not meet at least 1 eligibility criterion. The listing will present the eligibility criterion (or criteria if more than 1 deviation) that subjects did not meet and related comments, if collected.

Protocol deviations occurring after subjects entered the study are documented during routine monitoring. The number and percentage of subjects with important protocol deviations by deviation reason (e.g., nonadherence to study drug, violation of select inclusion/exclusion criteria) will be summarized by treatment group for All Randomized/Enrolled Analysis Set. A by-subject listing will be provided for those subjects with important protocol deviation.

Subjects who received study drug other than their treatment assignment at randomization or enrollment will be listed with the start and stop dates that they received incorrect study treatment.

A by-subject listing will be provided for subjects with important protocol deviation related to COVID-19. A separate listing will be provided for subjects with non-important protocol deviation related to COVID-19.

## 5. BASELINE CHARACTERISTICS

### 5.1. Demographics and Baseline Characteristics

Subject demographic variables (ie, age, sex, race, ethnicity and region [South Korea, Hongkong]) and baseline characteristics (body weight [in kg], height [in cm], body mass index [BMI; in kg/m^2]) will be summarized by HBeAg status (positive, negative) and overall for each treatment group and Group 1, 3, and 5 GS-9992 overall using descriptive statistics (n, mean, SD, median, Q1, Q3, minimum, and maximum) for continuous variables, and using number and percentage of subjects for categorical variables (Age : < 50 years, ≥ 50 years; BMI: < 18.5 kg/m^2, ≥ 18.5 kg/m^2 25 kg/m^2, ≥ 25 kg/m^2 30 kg/m^2, ≥ 30 kg/m^2). The summary of demographic data will be provided for the Safety Analysis Set.

A by-subject demographic listing, including the informed consent date, will be provided by subject ID number in ascending order.

### 5.2. Other Baseline Characteristics

Other baseline characteristics include

- HBV genotype
- cirrhosis (yes, no, indeterminate) and its determination method
- APRI as categories ( $\leq 1$ ,  $> 1$ )
- FibroTest score as a continuous variable and fibrosis stage by FibroTest score as a categorical variable (0.00 0.48, 0.49 0.74, 0.75 1.00)
- HBsAg (log10 IU/mL) as a continuous variable and as categories ( $\leq 4$  log10 IU/mL,  $> 4$  log10 IU/mL)
- HBV DNA (log10 IU/mL) as a continuous variable and as categories ( $< \text{LLOQ}$ ,  $\geq \text{LLOQ}$ ; and also  $< 7$  log10 IU/mL,  $\geq 7$  log10 IU/mL 8 log10 IU/mL,  $\geq 8$  log10 IU/mL)
- HBeAb (positive, negative)
- ALT (U/L) as a continuous variable and as categories based on central laboratory normal range ( $\leq \text{ULN}$ ,  $> \text{ULN}$  5 × ULN,  $> 5 \times \text{ULN}$  10 × ULN,  $> 10 \text{ ULN}$ )
- ALT level as categories based on American Association for the Study of Liver Diseases (AASLD) normal range with the ULN as 25 U/L for female and 35 U/L for male ( $\leq \text{ULN}$ ,  $> \text{ULN}$  5 × ULN,  $> 5 \times \text{ULN}$  10 × ULN,  $> 10 \text{ ULN}$ )
- current oral nucleoside/nucleotide treatment (Group 4 only)

- previous oral nucleoside/nucleotide treatment experience (yes, no)
- previous interferon experience to treat HBV (yes, no)
- duration of being HBV positive (years) as a continuous variable
- mode of HBV infection
- estimated glomerular filtration rate (eGFR) using the Cockcroft-Gault equation (mL/min)

eGFR will be calculated by the Cockcroft-Gault method:

$$\text{eGFR}_{\text{CG}} (\text{mL}/\text{min}) = \frac{[(140 - \text{age (years)}) \times \text{weight (kg)} \times (0.85 \text{ if female})]}{(\text{serum creatinine (mg/dL)} \times 72)}$$
, where weight is total body mass in kilograms.

These baseline characteristics will be summarized by HBeAg status (positive, negative) and overall for each treatment group and Group 1- 3, and 5 overall using descriptive statistics (n, mean, SD, median, Q1, Q3, minimum, and maximum) for continuous variables and using number and percentage of subjects for categorical variables. The summary of baseline characteristics will be provided for the Safety Analysis Set.

A by-subject listing of baseline characteristics will be provided by subject ID number in ascending order.

A by-subject data listing for HBV treatment history will be provided for the Safety Analysis Set. The listing will display the previous HBV treatment experience, previous HBV regimen and treatment, the treatment duration, and the reason for treatment discontinuation for treatment experienced subjects. For Group 4, a separate by-subject listing for current HBV treatment will be provided. The listing will present the current HBV treatment, regimen, and the start date of the current HBV treatment.

### **5.3. Medical History**

Medical history was collected at screening.

Data will be coded using the current version of Medical Dictionary for Regulatory Activities (MedDRA). Medical history will be summarized by system organ class (SOC) and preferred term (PT) by treatment group. Subjects who reported 2 or more medical history items that are coded to the same SOC and/or PT will be counted only once by the unique coded term in the summary. The summary will be provided for the Safety Analysis Set. No formal statistical testing is planned.

A by-subject listing will also be provided.

## 6. EFFICACY ANALYSES

### 6.1. Primary Efficacy Endpoint

#### 6.1.1. Definition of the Primary Efficacy Endpoint

The primary efficacy endpoint is the proportion of subjects with  $\geq 0.5 \log_{10}$  IU/mL decline in qHBsAg from baseline at Week 12.

#### 6.1.2. Statistical Hypothesis for the Primary Efficacy Endpoint

No statistical hypothesis testing will be performed.

#### 6.1.3. Analysis of the Primary Efficacy Endpoint

Proportion point estimates and the 2-sided 95% exact confidence intervals (CIs) of the primary efficacy endpoint will be provided by HBeAg status (positive, negative) and overall for each treatment group. CIs of the proportion point estimates will be constructed based on the Clopper-Pearson method {[Clopper 1934](#)}. CIs for the proportion differences by HBeAg status will be constructed based on the standardized statistic and inverting two 1 sided tests {[Chan 1999](#)}.

In addition, the proportion differences (Group 1 - Group 2, Group 3 - Group 2, Group 5 - Group 2) and the corresponding 2-sided 95% CIs will be reported. CIs of the proportion differences will be calculated by using stratum-adjusted Mantel-Haenszel (MH) proportions {[Koch 1989](#)}, stratified by the randomization stratification factor HBeAg status (positive, negative), as follows:

$$P_1 - P_2 \pm Z_{(1-\alpha/2)} * SE(P_1 - P_2),$$

where

- $(P_1 - P_2) = \frac{\sum w_h d_h}{\sum w_h}$ , is the stratum-adjusted MH proportion difference, where  $d_h = p_{1h} - p_{2h}$  is the proportion difference Groups 1 and 2 in stratum h (h = 1 and 2).
- $w_h = \frac{n_{1h} n_{2h}}{n_{1h} + n_{2h}}$ , is the weight based on the harmonic mean of sample size per treatment group for each stratum where  $n_{1h}$  and  $n_{2h}$  are the sample sizes of Groups 1 and 2 in stratum h.

- $SE(P_1 - P_2) = \sqrt{\frac{\sum w \left[ \frac{p_{1h}^* (1 - p_{1h}^*)}{n_{1h}} + \frac{p_{2h}^* (1 - p_{2h}^*)}{n_{2h}} \right]}{(\sum w_h)^2}}$ , where  $p_{1h}^* = \frac{m_{1h} + 0.5}{n_{1h} + 1}$  and  $p_{2h}^* = \frac{m_{2h} + 0.5}{n_{2h} + 1}$  and  $m_{1h}$  and  $m_{2h}$  are the number of subjects with  $\geq 0.5 \log_{10}$  IU/mL decline in HBsAg from baseline at Week 12 in Groups 1 and 2 in stratum h.

- $\alpha = 0.05$  for this study
- $Z_{(1-\alpha/2)} = Z_{0.975} = 1.96$  is the 97.5th percentile of the normal distribution

If the computed lower confidence bound is less than 1, the lower bound is defined as 1. If the computed upper confidence bound is greater than 1, then the upper bound is defined as 1.

#### 6.1.4. Subgroup Analysis of the Primary Efficacy Endpoint

No subgroup analysis will be performed.

### 6.2. Secondary Efficacy Endpoints

#### 6.2.1. Definition of Secondary Efficacy Endpoints

The secondary efficacy endpoints include the following:

- Proportion of subjects with  $\geq 1 \log_{10}$  IU/mL decline in qHBsAg from baseline at Week 12
- Proportion of HBeAg-positive subjects who achieve HBeAg loss and seroconversion through 48 weeks of treatment
- Proportion of subjects who achieve HBsAg loss through 48 weeks of treatment
- Proportion of subjects with drug resistance mutations during 48 weeks of treatment (Group 1 - 3, and 5)
- Change from baseline in HBV DNA and qHBsAg through 48 weeks of treatment (Group 1 - 3, and 5)
- Change from baseline in qHBsAg through 48 weeks of treatment (Group 4)
- Proportion of subjects experiencing HBV virologic breakthrough (2 consecutive visits of HBV DNA  $\geq 69$  IU/mL) during 12 weeks of GS-9992 treatment (Group 4)

### **HBV Serology definitions:**

- **HBsAg loss:** HBsAg changing from positive at baseline to negative at any postbaseline visit.
- **Confirmed HBsAg loss:** HBsAg loss confirmed by any 2 consecutive results.
- **HBsAg loss reversion:** Any postbaseline HBsAg positive result following HBsAg loss.
- **HBsAb seroconversion:** HBsAb changing from negative or missing at baseline to positive at any postbaseline visit.
- **Confirmed HBsAb seroconversion:** HBsAb changing from negative or missing at baseline to positive at any postbaseline visit confirmed by any 2 consecutive results.
- **HBsAb seroreversion:** Any postbaseline HBsAb negative result following HBsAb seroconversion.

HBeAg-related terminology is defined similarly.

Lower LOQ (LLOQ) for HBV DNA is defined as 20 IU/mL. LLOQ for qHBsAg is defined as 0.05 IU/mL. LLOQ for qHBeAg is defined as 0.11 IU/mL.

Missing data will be treated as a non-event unless otherwise specified (eg, no HBsAg loss, no seroconversion, etc.)

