### 8.3. Data Handling Conventions

For the primary efficacy endpoint and the categorical secondary efficacy endpoints, missing data will be handled using a missing = failure approach.

For the drug resistant mutations endpoint, a missing = excluded approach will be employed.

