## 1.2. Study Design

This is a Phase 2, randomized, open-label, active-controlled study to evaluate the safety and antiviral activity of GS-9992 plus TAF or commercially available NUC in CHB subjects.

Approximately 120 chronic, immune-active, HBV-infected adults without cirrhosis will be enrolled; including 100 viremic subjects not currently on HBV NUC and 20 virally suppressed subjects on a commercially available NUC.

**Groups 1 and 2:** Approximately 40 viremic subjects will be randomized in a 3:1 ratio to the following:

- Group 1: Approximately 30 subjects will be administered GS-9992 50 mg (2 × 25 mg capsules) once daily one hour before or one hour after a meal plus TAF 25 mg once daily with food for 12 weeks then TAF 25 mg once daily with food for 36 weeks
- Group 2: Approximately 10 subjects will be administered TAF 25 mg once daily with food for 48 weeks

Randomization will be stratified by HBeAg status (positive or negative) at screening with approximately 40% of HBeAg negative subjects enrolled.

**Group 3:** Approximately 30 viremic subjects will be administered GS-9992 200 mg (2 x 100mg) once daily one hour before or one hour after a meal plus TAF 25 mg once daily with food for 12 weeks then TAF 25 mg once daily with food for 36 weeks.

Approximately 40% of subjects enrolled in Group 3 will be HBeAg negative.

[figure not shown]
**Group 4:** Approximately 20 virally suppressed subjects currently being treated with a commercially available NUC(s) for CHB will be administered GS-9992 100 mg tablet once daily one hour before or one hour after a meal for 12 weeks.

Approximately 50% of subjects enrolled in Group 4 will be HBeAg negative. Subjects will remain on their current commercially available NUC(s) therapy for the duration of the study. All subjects will be followed through Week 48.

**Group 5 (Hong Kong):** Approximately 30 viremic subjects may be enrolled and assigned:

GS-9992 400 mg (2 x 200 mg tablets) once daily one hour before or one hour after a meal plus TAF 25 mg once daily with food for 12 weeks then TAF 25 mg once daily with food for 36 weeks.

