For Group 4, the proportion of subjects who experienced HBV virologic breakthrough (2 consecutive visits of HBV DNA  $\geq 69$  IU/mL) during 12 weeks of GS-9992 treatment will be evaluated by HBeAg status (positive, negative) and overall. Proportion point estimates and the 2-sided 95% exact CIs will be calculated based on the Clopper-Pearson method.

Imputation rules described in Section 3.6.1 will be used to assign HBeAg and HBsAg status for borderline results. Otherwise, a Missing Excluded analysis will be performed.

Plots of the mean  $\pm$  SD and median (Q1, Q3) of absolute values and changes from baseline in HBV DNA (Group 1- 3, 5) and qHBsAg will be presented (Group 1-5).

Drug resistance mutations will be analyzed as part of the Virology Study Report.

CCI

[REDACTED]

[REDACTED]

[REDACTED]

[REDACTED]

[REDACTED]

[REDACTED]

**CCI** [REDACTED]

[REDACTED]

[REDACTED]

[REDACTED]

[REDACTED]

[REDACTED]

[REDACTED]

[REDACTED]

[REDACTED]

[REDACTED]

[REDACTED]

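### Group 4 virologic breakthrough: the SAP carries two missing-data rules without saying which governs, and neither delivers the protocol's missing = failure if failure means breakthrough

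*SAP*

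**What the plan says.** Protocol 8.3 sets the general rule: "For the primary efficacy endpoint and the categorical secondary efficacy endpoints, missing data will be handled using a missing = failure approach". It makes one exception: "For the drug resistant mutations endpoint, a missing = excluded approach will be employed".

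Breakthrough is a Group 4 secondary endpoint in Protocol 3.1 and 8.1.3, and SAP 6.2.1 lists it as "Proportion of subjects experiencing HBV virologic breakthrough". It requires HBV DNA of at least 69 IU/mL at two visits in a row within the 12 weeks of GS-9992. It is categorical and is not in the exception. Group 4 is described in SAP 1.2 as "Approximately 20 virally suppressed subjects currently being treated with a commercially available NUC(s) for CHB".

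The SAP has two missing-data statements that could reach this endpoint:

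- SAP 6.2.1, closing the block of HBV serology definitions: "Missing data will be treated as a non-event unless otherwise specified (eg, no HBsAg loss, no seroconversion, etc".
- SAP 6.2.2. The analysis paragraph opens "For Group 4, the proportion of subjects who experienced HBV virologic breakthrough" and specifies exact intervals, by HBeAg status and overall. The paragraph after it refers to the rules for borderline serology and then says "Otherwise, a Missing Excluded analysis will be performed".

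SAP 6.4, which lists changes from the protocol's efficacy analyses, mentions only that the pharmacokinetic analysis was dropped.

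**The concern.** For HBsAg loss, HBeAg loss, seroconversion or HBsAg decline the event is the good outcome, so scoring missing data as a non-event is the same as scoring it as a failure. Breakthrough is a bad outcome. Scoring missing data as a non-event then gives the subject the favourable result, and excluding the subject removes the question from the denominator. If the protocol's failure means breakthrough, neither SAP rule does what the protocol asks, and the departure is not declared.

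In the SAP text that is not redacted, breakthrough is the only efficacy summary of HBV DNA in Group 4. The change-from-baseline tables and plots for HBV DNA in section 6.2.2 cover Groups 1-3 and 5. A favourable scoring rule would therefore not show up as a discrepancy with another Group 4 HBV DNA efficacy table. The study is also open label, so a rule left unsettled could be chosen with results in view.

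**Working it through.** The documents give no expected breakthrough rate, no dropout rate and no power calculation, so there is no plan figure to reproduce. The check compares the three rules using the SAP's own estimator.

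**Inputs.** n = 20 (SAP 1.2). About half HBeAg negative, so about 10 per stratum (SAP 1.2). Two-sided 95% Clopper-Pearson interval (SAP 6.2.2). Let b be the number of observed breakthroughs and d the number whose status cannot be determined. Both are assumed: b = 0 or 1, d = 1 to 4.

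**Estimates.**

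- Non-event (SAP 6.2.1): b/n
- Excluded (SAP 6.2.2): b/(n − d)
- Missing = failure, failure read as breakthrough (Protocol 8.3): (b + d)/n

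**Direction.** Protocol minus non-event is d/n, so each undetermined subject is worth 1/20 = 5 points. Protocol minus excluded is d(n − b − d)/[n(n − d)], which is never negative. Both SAP rules therefore sit at or below the protocol rule.

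**Intervals.** For x events in n, the limits are the 2.5% quantile of Beta(x, n − x + 1) and the 97.5% quantile of Beta(x + 1, n − x). For x = 0 the lower limit is 0 and the upper is 1 − 0.025^(1/n): 16.8% for n = 20 and 18.5% for n = 18.

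| b | d | Non-event | Excluded | Missing = failure (as breakthrough) |
|---|---|---|---|---|
| 0 | 1 | 0/20 = 0% (0 to 16.8) | 0/19 = 0% (0 to 17.6) | 1/20 = 5.0% (0.1 to 24.9) |
| 0 | 2 | 0/20 = 0% (0 to 16.8) | 0/18 = 0% (0 to 18.5) | 2/20 = 10.0% (1.2 to 31.7) |
| 0 | 3 | 0/20 = 0% (0 to 16.8) | 0/17 = 0% (0 to 19.5) | 3/20 = 15.0% (3.2 to 37.9) |
| 0 | 4 | 0/20 = 0% (0 to 16.8) | 0/16 = 0% (0 to 20.6) | 4/20 = 20.0% (5.7 to 43.7) |
| 1 | 2 | 1/20 = 5.0% (0.1 to 24.9) | 1/18 = 5.6% (0.1 to 27.3) | 3/20 = 15.0% (3.2 to 37.9) |

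In an HBeAg stratum of 10 with b = 0 and d = 1 the three results are 0/10 (upper limit 30.8%), 0/9 (33.6%) and 1/10 = 10% (0.3 to 44.5%).

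**Who is affected.**

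- Two consecutive observed values of at least 69 IU/mL: a breakthrough under every rule.
- One value of at least 69 IU/mL at Week 8 and no usable later sample: no breakthrough under 6.2.1, dropped under 6.2.2, breakthrough under missing = failure.
- Suppressed to Week 4 and no later sample: split in the same way, although nothing observed points to loss of control.

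**The case against.** A reader might infer that the SAP scores every Group 4 dropout as free of breakthrough, so that a subject who leaves with rising HBV DNA is reported as a success. The documents do not support that, for these reasons:

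- The non-event sentence is not shown to govern. It closes the serology block, its examples are serology events, and it gives way where something else is specified. The exclusion sentence stands nearer the breakthrough analysis and may be that other specification. Under it the dropout is removed, not credited.
- Rising HBV DNA that is seen twice counts under any rule. Protocol 6.6 asks sites to keep subjects who stop dosing in the study, and the early discontinuation visit samples HBV DNA. That sample may supply the second value, depending on its timing and visit window. Group 4 also stays on its NUC, and under SAP 3.8.2 data remain on-treatment until 3 days after the later of the GS-9992 and NUC stop dates.
- Protocol 8.3 does not define failure for an unfavourable event. Protocol 8.5.2 reports subjects who meet the endpoint. If failure meant not meeting it, missing = failure and missing = non-event would agree. Reading failure as breakthrough is the natural conservative choice, but it is an inference.
- The documents give no dropout rate or reasons for this trial, so nothing shows that undetermined subjects would be those losing viral control.

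These points narrow the concern but do not remove it. Excluding subjects is not missing = failure on either reading, and the SAP still does not say which of its two rules applies or how one unconfirmed value of at least 69 IU/mL is classified.

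**Conclusion.** The point holds in a limited form. The SAP has two missing-data rules that could apply to Group 4 breakthrough, does not choose between them, and does not list a departure from Protocol 8.3. If failure is read as breakthrough, both rules give a rate at or below the protocol's.

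The gap from the non-event rule is 5 percentage points per undetermined subject. With none observed, the gap from exclusion is the same, because both SAP rules then give 0%. The two SAP rules differ little from each other. These sizes rest on assumed counts of undetermined subjects and on that reading of failure. Only subjects without enough HBV DNA values to settle their status are affected.

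The importance is modest. The endpoint is secondary and descriptive, in about 20 subjects without a control group, and SAP 3.5 plans no hypothesis test. It is still worth correcting, because the rule can decide whether the reported rate is zero.

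**What to change.** 1. In SAP 6.2.1, limit the non-event rule to favourable events: HBsAg or HBeAg loss, seroconversion and HBsAg decline.
2. In SAP 6.2.2, state that the exclusion sentence does not apply to breakthrough.
3. Analyse breakthrough with missing = failure as Protocol 8.3 requires, and define failure as breakthrough. A subject with undetermined status then counts as a breakthrough, including one whose last available value is at least 69 IU/mL with no later sample. State which missing visits leave status undetermined. These definitions add to Protocol 8.3, which is silent on both, and should be presented as such.
4. Show the observed-only result as a second row.
5. List any remaining departure from Protocol 8.3 in SAP 6.4.

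The cost is a few sentences and one table row. The downside is that the reported rate can only be equal or less favourable, and it may overstate breakthrough for subjects who left while suppressed. The observed-only row lets the reader see how much.

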#### **6.2.2. Analysis Methods for Secondary Efficacy Endpoints**

The proportion of subjects with  $\geq 1 \log_{10}$  IU/mL decline in HBsAg from baseline at Week 12 will be analyzed on FAS similarly to the primary efficacy endpoint. Proportion point estimates and the 2-sided 95% exact CIs will be provided by HBeAg status (positive, negative) and overall for each treatment group. CIs of the proportion point estimates will be constructed based on the Clopper-Pearson method. In addition, the proportion differences (Group 1 - Group 2, Group 3 - Group 2, and Group 5 - Group 2) and the corresponding 2-sided 95% CIs will be reported. CIs of the proportion differences will be calculated by using stratum-adjusted MH proportions, stratified by HBeAg status (positive, negative).

A summary table will be provided for HBsAg-related serology results. The proportion of subjects who have ever had HBsAg loss, confirmed HBsAg loss, on-treatment HBsAg loss, posttreatment HBsAg loss (for subjects with positive HBsAg at the end of the on-treatment period), HBsAg loss with HBsAb seroconversion, HBsAg loss with HBsAb seroreversion, and HBsAg loss reversion with or without HBsAb seroconversion will be summarized by HBeAg status (positive, negative) and overall for each treatment group.

Additional summary tables may be provided for the following:

If  $\geq 3$  subjects achieved HBsAg loss,

- The proportion of subjects with HBsAg loss will be summarized by visit through Week 48;

If  $\geq 3$  subjects achieved HBsAg loss with HBsAb seroconversion,

- The proportion of subjects with HBsAb seroconversion will be summarized by visit through Week 48
- The proportion of subjects who have ever had HBsAg loss with HBsAb seroconversion, confirmed HBsAb seroconversion, on-treatment HBsAb seroconversion, posttreatment HBsAb seroconversion (for subjects with negative or missing HBsAb at the end of the on-treatment period) will be summarized.

For subjects in the FAS with baseline HBeAg status positive, similar summary tables will be provided for HBeAg-related serology results.

Summary statistics will be presented by HBeAg status (positive, negative) and overall for each treatment group for absolute values and change from baseline in HBV DNA ( $\log_{10}$  IU/mL) (Group 1- 3, and 5) and qHBsAg ( $\log_{10}$  IU/mL) by visit (Group 1- 5).

For Group 4, the proportion of subjects who experienced HBV virologic breakthrough (2 consecutive visits of HBV DNA  $\geq 69$  IU/mL) during 12 weeks of GS-9992 treatment will be evaluated by HBeAg status (positive, negative) and overall. Proportion point estimates and the 2-sided 95% exact CIs will be calculated based on the Clopper-Pearson method.

Imputation rules described in Section 3.6.1 will be used to assign HBeAg and HBsAg status for borderline results. Otherwise, a Missing Excluded analysis will be performed.

Plots of the mean  $\pm$  SD and median (Q1, Q3) of absolute values and changes from baseline in HBV DNA (Group 1- 3, 5) and qHBsAg will be presented (Group 1-5).

Drug resistance mutations will be analyzed as part of the Virology Study Report.

CCI

[REDACTED]

[REDACTED]

[REDACTED]

[REDACTED]

[REDACTED]

[REDACTED]

**CCI** [REDACTED]

[REDACTED]

[REDACTED]

[REDACTED]

[REDACTED]

[REDACTED]

[REDACTED]

[REDACTED]

[REDACTED]

[REDACTED]

[REDACTED]

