### **3.6. Missing Data and Outliers**

#### **3.6.1. Missing Data**

In general, missing data will not be imputed unless methods for handling missing data are specified. Exceptions are presented in this document.

A missing baseline laboratory result will be treated as normal (ie, no toxicity grade) for the laboratory abnormality summary.

Both the baseline and post-baseline borderline results for HBeAg, hepatitis B e antibody (HBeAb), HBsAg, and hepatitis B surface antibody (HBsAb) will be imputed following the rules below:

- HBsAb/HBeAb borderline → HBsAb/HBeAb negative
- HBsAg/HBeAg borderline → HBsAg/HBeAg positive

For missing last dose date of study drug, imputation rules are described in Section 3.8.1. The handling of missing or incomplete dates for adverse event (AE) onset is described in Section 7.1.5.2, and for prior and concomitant medications in Section 7.4.

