**6.4. Changes From Protocol-Specified Efficacy Analyses**

One of the secondary objectives of this study for Groups 1-3 and 5:

To characterize steady-state pharmacokinetics (PK) of study drugs

GS-9992 drug development was stopped by Spring Banks and the study team decided not to perform PK analysis and the collected PK samples will be stored.

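### SAP 6.2.2 adds a missing-excluded rule with no stated scope; read where it stands, it departs from SAP 6.2.1 and Protocol 8.3 for categorical serology endpoints, and SAP 6.4 does not declare it

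*SAP*

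**What the plan says.** Protocol 8.3 has two rules. The general one is "For the primary efficacy endpoint and the categorical secondary efficacy endpoints, missing data will be handled using a missing = failure approach". The single exception is "For the drug resistant mutations endpoint, a missing = excluded approach will be employed".

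The SAP has three relevant statements:

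- SAP 3.6.1, as the general default: "In general, missing data will not be imputed unless methods for handling missing data are specified".
- SAP 6.2.1, at the end of the serology definitions: "Missing data will be treated as a non-event unless otherwise specified (eg, no HBsAg loss, no seroconversion, etc".
- SAP 6.2.2, after the Group 4 breakthrough paragraph and a sentence on how borderline HBeAg and HBsAg results are classified: "Otherwise, a Missing Excluded analysis will be performed".

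The 6.2.2 sentence names no endpoint. The paragraph after it describes plots of HBV DNA and qHBsAg. Resistance mutations, the one endpoint for which the protocol prescribes exclusion, are sent to the separate Virology Study Report.

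SAP 6.4, which lists changes from the protocol's efficacy analyses, has one entry: "the study team decided not to perform PK analysis and the collected PK samples will be stored". It records no change to missing-data handling.

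**The concern.** The nearest thing for *otherwise* to refer back to is HBeAg and HBsAg status. On that reading, a result that is missing, as opposed to borderline, drops the subject from the denominator. HBsAg loss, HBeAg loss and HBeAg seroconversion are categorical secondary endpoints, so Protocol 8.3 would count that subject as a failure, and SAP 6.2.1 gives the same count by calling it a non-event.

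Two programmers working from the same SAP could therefore produce different denominators for the same table. One of those tables would depart from the protocol without being declared. Exclusion can only leave a response rate unchanged or raise it, so the undeclared version is the more favourable one.

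Group 4 breakthrough is exposed in a second way. It is an unfavourable event, so *failure* in Protocol 8.3 and *non-event* in SAP 6.2.1 need not mean the same thing, and no text gives breakthrough a rule of its own.

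**Working it through.** The plan gives no figure to reproduce on this point: there is no power calculation and no assumed dropout rate. The check is a comparison of texts, followed by an illustration of size.

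**Rule by rule**

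| Endpoint | Protocol 8.3 | SAP 6.2.1 | SAP 6.2.2, read where it stands |
|---|---|---|---|
| HBsAg loss | failure | non-event (own example) | excluded |
| HBeAg loss/seroconversion | failure | non-event (HBeAg terms defined in the same way) | excluded |
| Group 4 breakthrough | failure, direction not stated | non-event, if the default reaches it | possibly excluded |
| Continuous HBV DNA, qHBsAg | no rule | not addressed | excluded |
| Resistance mutations | excluded | not addressed | sent to the Virology Study Report |

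The first two rows disagree. The third is unsettled. The last two raise no difficulty.

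**Size for serology**

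With x events, n subjects and m missing, the rate is x/n under failure or non-event and x/(n − m) under exclusion. The planned numbers of HBeAg-positive subjects are 60% of 30 = 18 in each of Groups 1, 3 and 5, 60% of 10 = 6 in Group 2, and 50% of 20 = 10 in Group 4. Event and missing counts below are assumptions.

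| HBeAg loss | Full denominator | 1 excluded | 2 excluded | 3 excluded |
|---|---|---|---|---|
| Group 1, 2 events | 2/18 = 11.1% | 2/17 = 11.8% | 2/16 = 12.5% | 2/15 = 13.3% |
| Group 2, 1 event | 1/6 = 16.7% | 1/5 = 20.0% | 1/4 = 25.0% | 1/3 = 33.3% |
| Group 4, 1 event | 1/10 = 10.0% | 1/9 = 11.1% | 1/8 = 12.5% | 1/7 = 14.3% |

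The only guide to m in the documents is Protocol Table 1-2. In the HBeAg-positive TAF study, 27 of 581 TAF subjects (4.6%) had no Week 48 virologic data, and 18 × 27/581 = 0.84. That figure concerns HBV DNA in another trial, so it is a loose guide: about one missing per 18.

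**Size for Group 4 breakthrough**

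n = 20, exact 95% intervals, 1 event and 2 missing assumed:

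- non-event: 1/20 = 5.0% (0.1 to 24.9)
- excluded: 1/18 = 5.6% (0.1 to 27.3)
- missing counted as breakthrough: 3/20 = 15.0% (3.2 to 37.9)

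The direction given to *failure* matters more here than the choice between non-event and exclusion.

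**Which tables are affected**

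In the tables of subjects who ever had an event, one missed visit need not make the outcome missing, so the rules differ little. In by-visit tables they differ at every missed visit.

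By-visit tables are optional and tied to at least 3 responders. For HBeAg, SAP 6.2.2 says "similar summary tables will be provided for HBeAg-related serology results". If the TAF rate in Protocol Table 1-3 (78/565 = 13.8%) held for all 60 planned HBeAg-positive subjects in Groups 1-3 and 5, the expected count is 60 × 0.138 = 8.3, and the binomial chance of at least 3 is 99%.

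For HBsAg loss at 0.7%, the expected count is 0.42 and the chance is 0.9%. That calculation leaves out Group 4 and takes no loss in HBeAg-negative subjects, as the protocol reports for the HBeAg-negative TAF study. The HBeAg by-visit tables are therefore where a difference would most likely be seen.

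**The case against.** The best defence is that the texts can be reconciled. SAP 3.6.1 imputes nothing unless a method is specified, and SAP 6.2.1 specifies one for serology. Protocol 8.3 is silent on continuous secondary endpoints, and the paragraph after the disputed sentence is about plots of HBV DNA and qHBsAg. On that view *otherwise* covers the continuous summaries only. SAP 6.2.1 also carries an exception clause, so it is not an absolute rule. Its default is loosely worded and sits just below the HBV DNA quantitation limit, so it may reach breakthrough too.

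Much of this stands. A reader might infer that SAP 6.2.1 and 6.2.2 flatly contradict each other. The documents do not support that, because the continuous-only reading removes the conflict.

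That reading is nowhere stated, though, and the text immediately before the sentence concerns categorical outcomes. Treating the sentence as the exception that SAP 6.2.1 allows does not help: it would cancel that section's own examples and still depart from Protocol 8.3. The unclear direction of *failure* for breakthrough comes from the protocol, but the SAP is the place to settle it.

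**Conclusion.** The point holds as a minor one. SAP 6.2.2 states a rule without a scope. On its natural antecedent, that rule contradicts Protocol 8.3 for the serology endpoints and SAP 6.2.1's own examples, and SAP 6.4 does not declare it. The departure is conditional on that reading; the lack of scope is not.

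The shift is about 1 to 2 percentage points in a group of 18 with 1 to 3 missing. It is larger in Group 2, where one excluded subject of 6 moves 16.7% to 20.0%. These sizes rest on planned enrolment and assumed counts. The endpoints are secondary and descriptive, and the SAP tests no hypothesis.

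A reader might also infer that the rule reaches the primary endpoint or the 1 log10 HBsAg decline. The documents do not support this. The sentence stands in the section on secondary endpoints, and the 1 log10 endpoint "will be analyzed on FAS similarly to the primary efficacy endpoint". Nor does anything in the documents show that exclusion was intended in order to raise response rates.

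**What to change.** In SAP 6.2.2:

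- Limit Missing Excluded to the continuous by-visit HBV DNA and qHBsAg summaries and plots. Note that resistance, also missing = excluded under Protocol 8.3, is handled in the Virology Study Report.
- State that HBsAg loss (FAS) and HBeAg loss/seroconversion (FAS subjects HBeAg-positive at baseline) use missing = failure, that is non-event, with the full denominator, in both the ever-had and the by-visit tables.
- Give Group 4 breakthrough one missing-data rule with its direction, and keep all treated Group 4 subjects in the denominator.

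If exclusion really is intended for any categorical endpoint, list it in SAP 6.4 as a change from Protocol 8.3.

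The cost is SAP wording and table shells; no new data are needed. Some response rates would be slightly lower than under exclusion, for example 11.1% in place of 12.5%.
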